## **1.2.2 CODMAN ENTERPRISE® 2 Vascular Reconstruction Device**

The CODMAN ENTERPRISE VRD System and ENTERPRISE 2 VRD System serve the specific purpose of supporting a coil mass in a scenario where the shape of the aneurysm does not do so naturally, by providing a scaffold to prevent coil protrusion into the parent vessel lumen. The ENTERPRISE 2 VRD System incorporates several minor modifications, bench top testing showed that it met or exceeded the same acceptance criteria as the ENTERPRISE VRD System.

The modifications are further described in Section 5.1.2. There is no change to the intended use as a result of the modifications.

## **1.3. Previous Codman Sponsored Clinical Studies**

### **1.3.1 Feasibility studies: United States and Europe**

Cordis Neurovascular/Codman Neuro, Inc., conducted two multi-center, prospective, non-randomized, feasibility studies evaluating the CODMAN ENTERPRISE® Vascular Reconstruction Device (stent) and Delivery System. The CODMAN ENTERPRISE stent size 4.5 X 22 mm was used in both of these studies. One study was conducted in Europe at three medical institutions and the other was conducted in the United States at five medical institutions. Both studies were conducted according to local regulatory requirements and in accordance with the principles of the Declaration of Helsinki as enforced at the time the study was conducted.

The studies demonstrated the safety and probable benefit of the CODMAN ENTERPRISE® Vascular Reconstruction Device and Delivery System to facilitate endovascular coil embolization of wide neck saccular or fusiform intracranial aneurysms. The studies involved a more rigorous design than studies involving the use of stents to treat intracranial aneurysms currently found in the literature. Notable study design features include the use of an independent Clinical Events Committee (CEC), the use of an independent angiographic core lab, independent neurological assessment, and collection of all adverse events, whether or not related to the device or procedure, confirmed via routine study monitoring.

#### **European Data**

The European clinical study began with the first implant on 19 December 2003. Thirty-one subjects were enrolled into the study. The database was closed on 01 February 2006.

Baseline data were collected on 31 subjects who enrolled into the study, which received the CODMAN ENTERPRISE stent and were followed through six months. The majority (87.1%) of the subjects was female, and the average age was 54.5 years. A medical history of hypertension was reported in 38.7% of the subjects enrolled and 25.8% had endocrine / metabolic disease. The most commonly reported neurological event was

subarachnoid hemorrhage (38.7%) and 16.1% had a history of cranial nerve palsy and pounding / pulsatile headache. Fourteen subjects (45.2%) had undergone a prior intracranial embolization procedure for their cerebral aneurysm.

All serious adverse events were reviewed and adjudicated by the independent Clinical Events Committee. Six subjects (16.1%) experienced one or more device or procedure related serious adverse events. Eighteen subjects experienced 25 adverse events that were judged by the site to be at least possibly related to the device or procedure. The majority of these events occurred within 30 days. Neurological assessments included NIH Stroke score, modified Rankin score and clinical neurological examination. Most subjects experienced no change or improved neurological assessment ratings from pre-procedure to six months.

The mean NIH Stroke score was 0.3 pre-procedure and was 0.3 at six months. The majority of subjects (96.8%) were rated Grade 0 or Grade 1 on the modified Rankin scale pre-procedure, and 96.7% of subjects were Grade 0 or Grade 1 at six months (a Rankin scale of "0" indicates no neurological disability).

Angiographic measurements were performed by an angiographic core lab. At pre-procedure, the mean aneurysm dome height and width was 6.3 mm and 7.0 mm, respectively. The mean neck width was 4.8 mm, and mean dome width-to-neck ratio was 1.47. The mean proximal/distal diameter of the parent vessel pre-procedure was 3.1/2.8, and 2.8/2.5 at six months.

The technical success measures were also assessed using the angiographic core lab. Successful stent placement angiographically assessed immediately post-procedure was 96.8%. Successful stent placement was defined as stable stent placement with complete coverage across the aneurysm neck and parent artery patency, while satisfactory coil mass position was defined as stent maintains coil position within the sac with parent artery patency. Procedural success, defined as successful stent placement with satisfactory coil mass position without occurrence of procedural serious adverse events, was 90.0%. Maintenance of coil mass position was 96.7% at six months. The mean percent aneurysm occlusion post-procedure was 93.0% and 93.9% at six months.

### **United States Data**

The US clinical study includes data on subjects enrolled between 22 June 2004 and 12 October 2004. Subjects were followed for six months. The database was closed on 13 July 2005.

Baseline data were presented on 30 subjects who enrolled into the study and on 28 subjects who received the CODMAN ENTERPRISE stent and followed through six months. Two subjects were enrolled into the study but did not receive the device due to pre-procedure angiographic disqualification. In one case, the parent vessel was too large in diameter

and in the other, the aneurysm neck was too wide. The majority (76.7%) of the subjects was female, and the average age was 57.8 years. A medical history of hypertension was reported in 66.7% of the subjects enrolled and 40.0% had cardiovascular disease. The most commonly reported neurological event was pounding/pulsatile headache (43.3%) and 26.7% had a history of Altered Mental Status. Five subjects (16.7%) had previously suffered a subarachnoid hemorrhage, and 23.3% of the subjects had undergone a prior intracranial embolization procedure for their cerebral aneurysm.

All serious adverse events were reviewed and adjudicated by the Clinical Events Committee. Seven subjects (25%) experienced one or more device or procedure related serious adverse events. One subject died as a result of an intracerebral hemorrhage post-operatively. This death was classified as secondary to the presenting intracerebral hemorrhage. Eighteen subjects experienced 47 other adverse events that were judged to be at least possibly related to the device or procedure. The majority of these events occurred within 30 days.

Neurological assessments included NIH Stroke score, modified Rankin score and clinical neurological examination. Most subjects experienced no change or improved neurological assessment ratings from pre-procedure to six months.

The mean NIH Stroke score was 1.4 pre-procedure and was 0.3 at six months. This indicates that there was benefit for both neurological and overall clinical improvement following treatment, since an NIH stroke scale core of "0" is an indication of being completely normal. The majority of subjects (75.9%) were rated Grade 0 or Grade 1 on the modified Rankin scale pre-procedure, and 80.7% of subjects were Grade 0 or Grade 1 at six months (a Rankin scale of "0" indicates no neurological disability).

Angiographic measurements were made by an angiographic core lab. At pre-procedure, the mean aneurysm dome height and width was 8.2 mm and 8.6 mm, respectively. The mean neck width was 5.3 mm, and mean dome width-to-neck ratio was 1.43. The mean proximal/distal diameter of the parent vessel pre-procedure was 3.4/3.0, and 3.3/2.9 at six months.

The technical success measures were also assessed using the angiographic core lab. Successful stent placement with satisfactory coil mass position assessed immediately post-procedure was 100%. Successful stent placement was defined as stable stent placement with complete coverage across the aneurysm neck and parent artery patency, while satisfactory coil mass position was defined as stent maintains coil position within the sac with parent artery patency. Maintenance of coil mass position was 95.8% at six months. The mean post-procedure percent aneurysm occlusion was 87.9%, and improving to 92.0% at six months.

### **1.3.2 Feasibility study: Argentina**

A Feasibility Study of the Codman Neurovascular Self Expanding Stent System in Intracranial Arteries was conducted in Argentina. This was a prospective, single-arm, single-center study sponsored by Codman Neuro. The study was completed 09 March 2009.

The purpose of the study was to assess both effectiveness and safety. The CODMAN ENTERPRISE stent size 4.5 X 22 mm was used in this study. The two components of the effectiveness evaluation include:

**a) Technical feasibility**

For all subjects with a deployed stent:

- Successful stent placement/coil mass position angiographically assessed immediately post-procedure, and
- Evaluation of the percent occlusion assessed immediately post-procedure and at six months after treatment.

**b) Clinical/neurological outcome**

For all subjects with a deployed stent, clinical/neurological outcome using independent neurological evaluations (NIH Stroke Scale, Modified Rankin Scale) by independent, qualified personnel immediately after the procedure, at discharge, at thirty days and six months after treatment compared to the baseline evaluation.

### **Safety**

#### **Adverse Events (AEs)**

For all enrolled subjects, incidence of AEs assessed immediately following the pre-procedure angiogram through hospital discharge.

For subjects with a deployed stent, incidence of AEs assessed immediately following the pre-procedure angiogram through hospital discharge, at thirty days and six months after treatment.

#### **Results:**

Ten (10) subjects were enrolled, all of whom were entered into the study and evaluable at the 6 month follow-up.

#### **Effectiveness:**

This study demonstrated the technical feasibility of the CODMAN ENTERPRISE system for the treatment of wide-necked intracranial aneurysms. Stable stent placement with complete neck coverage and parent artery patency post-procedure was observed in 9/10 (90%) subjects; since due to poor angiographic image quality the Core Lab was unable to confirm stable stent placement immediately post-procedure and therefore this one subject was reported not to have stable stent placement immediately post-procedure. Immediately post-procedure and at the 6 month follow-up, the

stent was reported to maintain coil mass position within the aneurysm sac with parent artery patency in 10/10 (100%) subjects.

The mean post-procedure aneurysm occlusion was 86.8%, and improved to 88.8% at six months.

### **Safety:**

The CODMAN ENTERPRISE system was demonstrated to be safe for the treatment of wide-necked aneurysm in this study population. Only 3 SAEs were reported in 3 subjects, and no SAEs were reported to be related to the device. There were no deaths and no event caused the stenting/coiling procedure to be discontinued.

#### **1.3.3 Study of ENTERPRISE in the Japanese Clinical Setting**

Johnson & Johnson Medical Company in Japan conducted a multicenter, single-arm study evaluating the CODMAN ENTERPRISE® Vascular Reconstruction Device. The study period was November 2007 through October 2008.

Since the probable benefit and safety of CODMAN ENTERPRISE had already been demonstrated in clinical studies in the United States and European countries, and since no device with similar functions of those to ENTERPRISE was commercially available, Japan conducted the study to evaluate the applicability of CODMAN ENTERPRISE assisted procedure in the Japanese clinical setting. In this study, procedural success was the primary endpoint in patients with a non-ruptured intracranial wide-neck (defined as a neck width  $\geq$  4 mm or a dome-to-neck ratio  $<$  2) saccular aneurysm with a greatest diameter of at least 10 mm that is refractory to surgeries (e.g., clipping) or coil-only embolization. Four stent sizes were used in the study (4.5 mm x 14 mm, 4.5 mm x 22 mm, 4.5 mm x 28 mm, or 4.5 mm x 37 mm) according to lesion findings. Fifteen (15) patients were enrolled and reported on in the study submission to the Shonin. It was approved in Japan on 08 January 2010 under the product name CODMAN ENTERPRISE Stent.

#### **1.3.4 Sunrise Registry: European Post Market Surveillance**

The Sunrise Registry is a multicenter, prospective, observational registry to evaluate the safety and performance of the CODMAN ENTERPRISE System in routine clinical practice.

This study demonstrates the safety and performance of the CODMAN ENTERPRISE System to facilitate endovascular coil embolization of wide neck saccular intracranial aneurysms. The study design featured the use of an angiographic core lab as well as study monitoring.

One hundred and nine (109) Subjects were enrolled in 15 centers (1 center in Australia and 14 centers in Europe) where the CODMAN ENTERPRISE

System is approved for commercial use. Three subjects who did not give consent prior to data entry are omitted from analysis (consent forms were signed after the procedure had been performed). One subject did not receive treatment and was excluded as well.

Data is presented on 105 subjects who were enrolled into the study and signed informed consent before stent placement. Per protocol, the study period for each subject was 6 months. The majority (71.6%) of the subjects was female, and the average age was 55.3 years. A medical history of hypertension was reported in 36.2% of the subjects enrolled and 3.8% had cardiovascular disease. The most commonly reported neurological event at baseline was TIA/CVA (20.0%), and 17.1% had a history of recurrent headaches. At baseline, 34.3% of the subjects had undergone a prior intracranial embolization procedure or clipping for their cerebral aneurysm.

All serious adverse events were adjudicated by the participating investigators. Based on the adjudication, two subjects experienced a device- or procedure-related serious adverse event for an estimated rate of 1.9%. Seventeen subjects (16.2%) experienced 17 at least possibly device or procedure adverse events (including the two SAEs reported above). The majority (70.6%) of these events occurred before hospital discharge.

Angiographic measurements were made by an angiographic core lab. At pre-procedure, the mean aneurysm dome height and width was 7.8 mm and 6.9 mm, respectively. The mean neck width was 4.9 mm. The mean proximal/distal diameter of the parent vessel pre-procedure was 3.6/3.3.

The technical success measures were also assessed using the angiographic core lab. Successful intracranial device placement (defined as stable CODMAN ENTERPRISE placement with complete coverage of the aneurysm neck and parent artery patency) was achieved in 85.7% of the cases. Satisfactory coil mass position (defined as CODMAN ENTERPRISE maintains coil position within the sac with parent artery patency as defined angiographically) was 83.5% immediately post-procedure and 83.3% at six months. Complete aneurysm occlusion was achieved in 20.2% of cases immediately post-procedure and in 58.2% of the subjects with 6 months follow-up.

#### **1.4. Commercial Approval of ENTERPRISE**

##### **"Conformité Européene" (CE-mark):**

Outside of the United States (U.S.), the CODMAN ENTERPRISE® Vascular Reconstruction Device and Delivery System and the CODMAN ENTERPRISE® 2 Vascular Reconstruction Device are released by meeting the European medical device regulations for use with occlusive devices in the treatment of intracranial aneurysms.

**Humanitarian Use Device (HUD) approved through Humanitarian Device Exemption (HDE) No. H060001:**

In the United States, the CODMAN ENTERPRISE® Vascular Reconstruction Device and Delivery System and the CODMAN ENTERPRISE® 2 Vascular Reconstruction Device are authorized by the Federal Law for use with embolic coils for the treatment of wide-neck, intracranial, saccular or fusiform aneurysms arising from a parent vessel with a diameter of  $\geq 2.5$  mm and  $\leq 4$  mm. Wide neck is defined as having a neck width  $\geq 4$  mm or a dome-to-neck ratio  $< 2$ .

**Japanese Government:**

In January 2010, Johnson & Johnson Medical Company in Japan received SHONIN approval from Japan's Ministry of Health, Labor and Welfare to market the CODMAN ENTERPRISE® Vascular Reconstruction Device and Delivery System in Japan.

## **2.0 STUDY OBJECTIVES**

The primary objectives of the study are to evaluate the safety (as assessed by rates of major ipsilateral stroke and/or death and in-stent stenosis) and effectiveness (as measured by the rate of complete angiographic occlusion) of ENTERPRISE when used in conjunction with endovascular coil embolization of unruptured wide-neck, intracranial, saccular anterior circulation aneurysms ( $\leq 10$  mm) in a prospective, multi-center, single arm clinical study.

Secondary effectiveness objectives include the evaluation of treatment outcomes for subjects treated with ENTERPRISE in the acute (procedure and immediate post-procedure time frames) and follow-up phases of patient management.

Secondary safety objectives include the evaluation of adverse safety outcomes for subjects treated with ENTERPRISE from the start of the procedure through the end of study participation (12 months or premature discontinuation of study participation).

In addition, the rates of stent movement and migration will be described.

## **3.0 STUDY DESIGN**

### **3.1 General Design**

This is a prospective, single arm, multicenter clinical study to evaluate the safety and effectiveness of the ENTERPRISE stent when used in conjunction with endovascular coil embolization in the treatment of unruptured wide-neck, saccular anterior circulation intracranial aneurysms ( $\leq 10$  mm) arising from a parent vessel with a diameter of  $\geq 2.5$  mm and  $\leq 4$  mm.

This study will be conducted at a maximum of 25 centers in the United States (US). The study will be registered and results will be reported to the U.S. database maintained by the United States National Institutes of Health (NIH) on the United States National Library of Medicine's ("NLM") website [www.clinicaltrials.gov](http://www.clinicaltrials.gov) under Title VIII of the Food and Drug Administration Act of 2007 ("FDAAA").

It is anticipated that fewer than 15% of entered subjects will be unevaluable at the 12 month follow-up visit due to loss to follow-up and/or missing primary angiographic occlusion or safety data. However, subjects with missing data at the time of endpoint analysis will have primary effectiveness and primary safety endpoint data imputed as last observation carried forward (LOCF). Subjects who receive the device but in whom there is no post-procedure data will be treated as failures for the primary effectiveness analysis; subjects who do not receive the device because of treatment failure due to reasons associated with the device will also be treated as failures. Subjects with no post-procedure endpoint data upon which to base a LOCF imputation will be excluded from the primary safety endpoint analyses; it is anticipated that fewer than 7% of MITT subjects will be excluded from either primary effectiveness or primary safety endpoint analyses. Thus, although the primary endpoint analyses will be in the Modified Intent to Treat (MITT) population for primary effectiveness and safety endpoints, up to 320 subjects will be enrolled to achieve approximately 300 subjects with post-procedure data in the MITT population. A group sequential design will be employed in which one primary endpoint interim analysis will be conducted after N=160 subjects have been enrolled and followed through 6 months post-procedure, to determine if the study should stop early for futility or tentative success; it is anticipated that there will be at least N=150 subjects with post-procedure data in the MITT population for this analysis. If the stopping rule is met for the trial to stop early for tentative success, a final confirmatory analysis will be conducted when all subjects have reached 12 months post-procedure. If the trial is not terminated early for futility or tentative success, then enrollment will continue up to the full enrollment sample size of N=320.

Patients who experience an AE of Special Interest and who have an MRS >2 at any clinical evaluation will be followed through 24 months post-procedure.

An independent core laboratory will perform the quantitative analysis for the primary and secondary effectiveness endpoints, as well as for subjects where the 12 month angiogram is an endpoint assessment. A medical monitor will adjudicate the relationship of AEs to the device, procedure, and/or underlying disease in accordance with the definitions specified within this protocol.

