#### 3.2.2.1 Incidence of Major Ipsilateral Stroke and/or Death

The incidence of a major ipsilateral stroke and/or death will be evaluated from the start of the index procedure until completion of the 12 month follow-up. A major ipsilateral stroke is defined as a new neurological event which is ipsilateral and in the vascular distribution territory of the stenting procedure and that results in an increase of  $\geq 4$  on the National Institute of Health Stroke Scale (NIHSS) as compared to baseline and persists for greater than 24 hours.

For a successful evaluation of this endpoint, the upper confidence limit of a 2-sided 95% confidence interval for the proportion of subjects who experience major ipsilateral stroke and/or death through 12 months post-procedure will be less than 25%.

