### **Primary Safety Endpoint: Incidence of Major Ipsilateral Stroke and/or Death**

For a successful evaluation of this endpoint, the upper confidence limit of a 2-sided 95% confidence interval for the proportion of subjects who experience major ipsilateral stroke and/or death through 12 months post-procedure will be less than 25% (regardless of whether this analysis is conducted at the interim analysis with N=160 subjects at 6 months follow-up or the final analysis with N=320 subjects at 12 months follow-up). The null and alternative hypotheses for this endpoint are as follows:

Null Hypothesis  $H_0$ :  $p_{\text{Major Stroke/Death}} \geq 25\%$

Alternative Hypothesis  $H_A$ :  $p_{\text{Major Stroke/Death}} < 25\%$

where  $p_{\text{Major Stroke/Death}}$  represents the proportion of subjects in the treatment population who experience major ipsilateral stroke/death.

**Decision Criterion:** The null hypothesis will be rejected and the alternative hypothesis will be concluded if the upper confidence limit of a 2-sided 95% confidence limit (normal approximation) is less than 25%.

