### **Statistical Power for Primary Safety Endpoints**

#### **Primary Safety Endpoint: Incidence of Major Ipsilateral Stroke and/or Death**

For a successful evaluation of this endpoint, the upper confidence limit of a 2-sided 95% confidence interval for the proportion of subjects who experience major ipsilateral stroke and/or death through 12 months post-procedure will be less than 25% (regardless of whether this

analysis is conducted at the interim analysis with N=160 subjects at 6 months follow-up or the final analysis with N=320 subjects at 12 months follow-up). The anticipated rate of major ipsilateral stroke and/or death in the population is not greater than 14%, so it is estimated that the statistical power to demonstrate this endpoint with a sample size of N=150 evaluable subjects (MITT subjects with post-procedure data) is approximately 92.5%. This power estimate was calculated with the following SAS code:

**SAS Code for Power Estimation:  
Incidence of Major Ipsilateral Stroke and/or Death**

```
proc power;
  onessamplefreq test=z method=normal
  nullproportion = 0.25
  proportion = .14
  alpha = 0.05
  sides = 2
  ntotal = 150
  power = .;
  title 'z Test, uses null proportion for
variance estimate';
run;
```

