10.4.1.2 Primary Safety Endpoints

- Incidence of major ipsilateral stroke and/or death

The incidence of major ipsilateral stroke and/or death will be evaluated from the start of the index procedure until the completion of the 12-Month Follow-up based on the assessment from DSMB adjudicated data.

The number and percentage of subjects with major ipsilateral stroke and/or death up to and including 12-Month Follow-up will be summarized.

- Incidence of In-sent stenosis

The number and percentage of subjects with in-stent stenosis up to and including 12 months post-procedure will be summarized based on the assessment from the Independent Core Laboratory. Subjects with missing data will be excluded from analysis.

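### The protocol's 25% stroke/death test uses LOCF on a crude proportion and so leans downward; the SAP drops that test but leaves the stroke/death denominator undefined

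*Protocol*

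**What the plan says.** **Protocol.** Section 3.2.2.1 makes stroke/death a cumulative outcome, "evaluated from the start of the index procedure until completion of the 12 month follow-up". The criterion is that the upper 95% limit for the "proportion of subjects who experience major ipsilateral stroke and/or death through 12 months post-procedure will be less than 25" percent. Section 9.7 rejects the null "if the upper confidence limit of a 2-sided 95% confidence limit (normal approximation) is less than 25" percent. No estimator that allows for censoring is named.

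Section 3.1 has missing "primary effectiveness and primary safety endpoint data imputed as last observation carried forward". Section 9.5 lets the carried value be as early as the immediate post-procedure evaluation. Only subjects with no post-procedure data leave the safety analysis (fewer than 7% expected). On overall loss, section 3.1 says: "It is anticipated that fewer than 15% of entered subjects will be unevaluable at the 12 month follow-up visit". That figure includes missing angiographic data.

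**SAP.** It was written after the decision to terminate for low enrollment. Sections 6 and 10.4 drop the hypothesis tests, section 10.5 drops the interim analysis and section 10.6 imputes nothing by default. Confidence intervals are kept but are not for inference. On stroke/death, section 10.4.1.2 says: "The number and percentage of subjects with major ipsilateral stroke and/or death up to and including 12-Month Follow-up will be summarized". No missing-data rule follows, although the in-stent stenosis item in the same section has one. The default in section 10.1 then applies: percentages rest on non-missing values, without missing data and without subjects who discontinued early.

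**The concern.** Carrying an angiographic reading forward assumes that a state persists. Carrying "no stroke, alive" forward assumes that nothing happened in a period when nobody looked. The subject stays in the denominator for the full 12 months and can add nothing further to the numerator. What is compared with 25% is therefore events seen before loss, which is at most the 12-month risk. On a primary safety goal that error favours the device.

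The SAP raises a different problem. If early discontinuations leave the denominator, a subject who has a major stroke and then withdraws may leave with the event. If only event-free discontinuations leave, the rate moves up instead. The reported percentage then depends on a choice the SAP does not make, and in a study closed early a few subjects can matter.

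**Working it through.** **1. Reproduce the plan's power.** Inputs from protocol 9.9: goal 25%, expected 14%, N=150, two-sided alpha 0.05, null-variance z test.

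- Null SE = √(0.25×0.75/150) = 0.0354; SE at 14% = √(0.14×0.86/150) = 0.0283.
- Power = Φ[(0.25 − 0.14 − 1.96×0.0354)/0.0283] = Φ(1.44) = 92.5%, as stated.

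**2. Pass limits under section 9.7.** Require x/n + 1.96√[(x/n)(1−x/n)/n] < 0.25.

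- N=150: 28 events pass (upper limit 24.9%); 29 fail (25.7%).
- N=300: 61 pass (24.9%); 62 fail (25.2%).
- With no loss, P(pass | true 25%) = P(X≤28; 150, 0.25) = 4.2% and P(X≤61; 300, 0.25) = 3.4%. These exceed 2.5% because of the normal approximation, which is a separate matter.

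**3. Share carried forward, d.** The 15% ceiling applies to entered subjects, and N=150 and N=300 are already net of subjects without post-procedure data. Assume the planned shortfalls (160−150 = 10 and 320−300 = 20) are such subjects.

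- 0.15×160 = 24; 24−10 = 14; 14/150 = 9.3%.
- 0.15×320 = 48; 48−20 = 28; 28/300 = 9.3%.

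**4. Effect at a true 25%.** Let f be the share of a carried-forward subject's 12-month risk that falls after last contact. With loss unrelated to risk, the crude rate is p(1 − d·f). The documents give no event timing, so f is an assumption.

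| d | f | Crude rate at p=25% | P(pass), N=150 | P(pass), N=300 |
|---|---|---|---|---|
| 0 | – | 25.0% | 4.2% | 3.4% |
| 9.3% | 0.25 | 24.4% | 5.8% | 5.5% |
| 9.3% | 0.5 | 23.8% | 8.0% | 8.6% |
| 9.3% | 1 | 22.7% | 14.1% | 18.6% |
| 15% | 0.25 | 24.1% | 7.1% | 7.2% |
| 15% | 0.5 | 23.1% | 11.4% | 14.0% |
| 15% | 1 | 21.3% | 25.4% | 38.0% |

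**5. Effect at the expected 14%.** Take 21/150 observed events. The crude upper limit is 0.14 + 1.96×0.0283 = 19.6%. Correct the rate to 0.14/(1−d·f), with effective N = 150(1−d·f).

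- d=9.3%, f=0.5: rate 14.7%, upper limit 20.5%.
- d=15%, f=1: rate 16.5%, upper limit 22.9%.

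All are below 25%.

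**6. The SAP denominator.** The final sample size is not given, so the planning figures serve only as illustration: 150 subjects, 21 events, 14 early discontinuations, e of the 21 events occurring before discontinuation.

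- Everyone kept: 21/150 = 14.0%.
- Discontinuations removed, e=0: 21/136 = 15.4%.
- Discontinuations removed with their events: e=2 gives 19/136 = 14.0%; e=3 gives 18/136 = 13.2%. Each event removed costs 1/136 = 0.7 points.

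The direction therefore depends on e and on how section 10.1 is read.

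**The case against.** The strongest reply is that the test no longer exists. The SAP drops it, drops the interim and imputes nothing, so a reader who infers that the final report will clear the 25% goal on flattered data is mistaken. That stands. Nor can the downward bias be carried over to the SAP: removing event-free discontinuations raises the percentage.

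The 15% rows of the table are also tempting and should not be taken as the expected effect. The 15% is a ceiling, it covers missing angiograms, and it overlaps with subjects already excluded. A value of f=1 would need carried-forward subjects to have had no risk during or just after the procedure. The protocol's own background points to early events: most device- or procedure-related adverse events fell within 30 days in the US and European feasibility studies, and 70.6% fell before discharge in the European registry. Those are related adverse events, not stroke/death alone, so they favour a low f without fixing it.

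A reader might also infer a larger bias from section 9.7, which would apply the same limit at the interim with 6-month follow-up. Section 9.11 confines the interim test to efficacy, and the SAP cancels it.

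Study success rests on effectiveness alone (section 9.7), and SAP section 5.4 reports that the Close Out Plan requires enrolled and treated subjects to complete 12-month visits, which should limit loss. Section 10.2 lists deaths separately from discontinuations, so the dropped-event risk is mainly for non-fatal stroke. None of this supplies the missing rule in SAP 10.4.1.2.

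Kaplan-Meier is not a full cure. It assumes uninformative censoring, so it does not correct for subjects with neurological trouble being lost more often.

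**Conclusion.** The point holds in two limited parts.

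- **Protocol 3.1, 9.5 and 9.7:** LOCF on a crude proportion biases 12-month stroke/death downward against the 25% goal. With about 9% carried forward, loss unrelated to risk and f between 0.25 and 0.5, the chance of passing at a true 25% rises from 4.2% to about 6-8% (N=150) and from 3.4% to about 5.5-9% (N=300). It is smaller with less loss or mostly peri-procedural events, and the expected 14% passes either way.
- **SAP 10.1 and 10.4.1.2:** the remaining defect is the unspecified handling of early discontinuations, which could drop a subject whose stroke came before withdrawal and makes the rate depend on the denominator chosen. Its size cannot be given without the final numbers.

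**What to change.** In SAP 10.4.1.2:

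- State that any subject with a major ipsilateral stroke or death before discontinuation stays in the analysis as an event, overriding the default in 10.1, and state the denominator.
- Beside the count and exact binomial interval, report descriptively a Kaplan-Meier 12-month cumulative incidence with 95% CI. Time runs from the start of the index procedure to first major ipsilateral stroke or death, censored at last clinical contact.
- Name in advance the day at which the curve is read, consistent with the 12-month window (Day 270-450 in the SAP, 320-410 in the protocol). Day 365 without further rules would omit later qualifying events and treat subjects seen just before it as censored.
- Note that the estimate assumes uninformative censoring.

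If the protocol test were ever reinstated, replace LOCF for this endpoint in 9.5 and 9.7 with the same estimator and require its upper 95% limit to be below 25%.

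The cost is wording and one standard SAS procedure, with no added subjects or visits. The interval becomes slightly wider and the estimate may be slightly less favourable.
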